6.1.9 Overall Survival (OS)

Overall survival is defined as from start of treatment until death due to any cause. Otherwise OS is censored on the last day patients are known to be alive.

6.1.10 The primary endpoint:

The 6-month PFS rate is the primary endpoint. The 6-month PFS is dichotomous, *yes* or *no*. Radiographic scan for disease measurement that is done within ± 14 days of the 6-month landmark (Day 182 since first receiving study drug) will be counted to determine the 6-month PFS status. Patients who are alive and progression-free at 6 months (182 days) since first starting regorafenib will be counted as 'yes' for the 6-month PFS. Patients who progress or die within 6 months of starting regorafenib will be counted as 'no' for the 6-month PFS. Patients whose status of progression or death at 6 months is unknown due to early withdrawal, loss-of-follow-up, or other reasons will be also counted as 'no' for 6-month PFS.

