5.2.4 One day of week 3 of Cycle 2 only

- Octreotide scan

5.2.5 One Day of Week 3 of every other Cycle (starting with Cycle 2)

- Serum Chromogranin
- Tumor Assessment

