5.4 Study Calendar

Cycles will be 28 Days. Regorafenib will be taken orally Days 1-21 of each Cycle. For first cycle all labs and EKG should be done within 7 days of first receiving study drug. For the first cycle, Imaging studies should be done within 28 days of first receiving study drug.

Parameter	Pre-Treatment ⁶	Day 1 of All Cycles ¹ ²	Day 8, Day 15 And 22 of Cycle 1 and 2 only ¹²	Day 15 of all Cycles ¹ ²	One Day of Week 3 Of every other Cycle (starting with Cycle 2)	Off study	Follow-up
Informed Consent	X						
Pill Diary		X				X	
History & Physical Exam	X	X					
Weight, SWOG Performance Status, Con Meds	X	X				X	
Adverse Event/Toxicity Evaluation	X	X					
WBC (differential), Hgb, Platelets	X	X		X			
Complete Metabolic Panel, Phosphorus, Magnesium, LDH	X	X	Liver function	X			
Lipase	X	X					
Thyroid Function (TSH, T3, T4)	X	X ³					
PT/PT-INR, PTT	X	X ^{3,9}					
Urinalysis for proteinuria	X	X					
5HIAA	X	X					
Serum Chromogranin	X				X		
Octreotide scan	X				Cycle 2 only		
EKG	X	X ³					
CXR (if CT of chest not done)	X ⁷				X ⁷		
BP Monitoring		X	X				
Radiology, x-ray or Scans for disease measurement ²	X ⁸				X		X ¹⁰
Archival tumor tissue	X ⁸						
Plasma	X ⁸					X ⁸	
Urine Pregnancy Test	X ⁵	X ⁵					
Survival Follow-up							X ¹¹

- 1 If used to follow measurable disease.
- 2 Within 28 days of Cycle 1, Day 1.
- 3 As clinically indicated.
- 4 Paraffin embedded tissue must be available for review.
- 5 For women of childbearing potential
- 6 Confirm response within 4 weeks.
- 7 Not required if CT scan of the chest is done.
- 8 See section 9. For plasma two purple top tubes to the [name] lab.
- 9 Close monitoring (day 5 of cycle 1 and day 1 of each cycle) of PT/PT-INR and PTT is mandatory for patients on agents such as warfarin and heparin.
- 10 Patients that come off for reasons other than disease progression will have their standard of care scans measured via RECIST until progressive disease, to determine date of disease progression
- 11 Patients will be followed up via phone call, medical records or database search until death to determine survival time
- 12 All study visits allow a +/- 7 day window

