6.1.4.3 Evaluation of Best Overall Response

The best overall response is the best response recorded from the start of the treatment until disease progression/recurrence (taking as reference for progressive disease the smallest measurements recorded since the treatment started). The patient's best response assignment will depend on the achievement of both measurement and confirmation criteria.

Target Lesions	Non-Target Lesions	New Lesions	Overall Response	Best Response for this Category Also Requires:
CR	CR	No	CR	≥4 wks. confirmation
CR	Non-CR/Non-PD	No	PR	≥4 wks. confirmation
PR	Non-PD	No	PR	
SD	Non-PD	No	SD	documented at least once ≥4 wks. from baseline

PD	Any	Yes or No	PD	no prior SD, PR or CR
Any	PD*	Yes or No	PD	
Any	Any	Yes	PD	
* In exceptional circumstances, unequivocal progression in non-target lesions may be accepted as disease progression.				

Note: Patients with a global deterioration of health status requiring discontinuation of treatment without objective evidence of disease progression at that time should be reported as “*symptomatic deterioration*”. Every effort should be made to document the objective progression even after discontinuation of treatment.

Note: If subjects respond to treatment and are able to have their disease resected, the patient’s response will be assessed prior to the surgery.

6.1.5 **Confirmation of Response:**

Confirmation of response is not required in this trial as response is not the primary endpoint.

6.1.6 **Duration of Response**

Duration of overall response: The duration of overall response is measured from the time measurement criteria are met for CR or PR (whichever is first recorded) until the first date that recurrent or progressive disease is objectively documented (taking as reference for progressive disease the smallest measurements recorded since the treatment started).

The duration of overall CR is measured from the time measurement criteria are first met for CR until the first date that recurrent disease is objectively documented.

Duration of stable disease: Stable disease is measured from the start of the treatment until the criteria for progression are met, taking as reference the smallest measurements recorded since the treatment started.

6.1.7 **Progression-Free Survival (PFS)**

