10.3 Data Analyses Plans

Two cohorts will be analyzed separately. The primary data analysis set will include all patients who enroll the study and start to receive regorafenib for decision making in accrual and warranting further studies. Patients who withdraw the study, are lost to follow-up, or start another therapy before the status of 6-month PFS is determined will be counted as 'no' for the primary endpoint and be included in the primary data analysis set. Patients who drop out the trial before starting regorafenib will be replaced and excluded from the primary data analysis set.

The primary endpoint, 6-month PFS rate will be summarized as a proportion of patients who are alive and progression-free among all patients in the primary data analysis set. The 95% confidence intervals of the 6-month PFS rate will be calculated using the Wilson method. We chose 6-month as the cut-off point because it would be easier to compare with the historical data. The tumor response will be evaluated by CT scans every 2 cycles starting with week 3 of cycle 2. Six-months since starting treatment are 182 days, may not be on the CT scan date. CT scans will not on the strict schedules. Additional scans may be conducted to confirm a complete or partial response. Patients whose systems deteriorate clinically will be counted as progression event without confirmation of CT scans. CT scans that are conducted within ± 14 days of the landmark Day 182 will be used to determine the 6-month PFS status if there are no other scans available to determine the status. The detailed status of 6-month PFS will be counted as follows: alive and progression-free, disease progression within 6 months, death within 6 months, and progression at 6 months unknown due to early withdrawal, toxicities, or other reasons.

A sensitivity analysis of PFS at week 24 will be conducted. The PFS rate at week 24 may provide the impact of CT scheduling on estimating the 6-month PFS rate.

In addition, progression-free survival (see definition at section 6.1.7) will be analyzed using Kaplan-Meier curves. The median PFS and 95% CIs will be calculated. The probability of 6-month PFS will be estimated from the KM curve too.

The secondary endpoints including tumor response rate and OS (see definition at section 6.1.9) will be analyzed descriptively.

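### On-schedule scans miss the Day 168–196 window that decides 6-month PFS, and Sections 6.1.10 and 10.3 do not agree on how to score the patients affected

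*Combined protocol and SAP*

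**What the plan says.** - **Landmark (6.1.10).** A scan within ±14 "days of the 6-month landmark (Day 182 since first receiving study drug) will be counted to determine the 6-month PFS status". Alive and progression-free at Day 182 is a success; progression or death within 6 months is a failure. Status unknown because of withdrawal, loss to follow-up or other reasons is also a failure.
- **Scan calendar (5.2.5, 5.4, 10.3).** Section 5.2.5 places tumour assessment on "One Day of Week 3 of every other Cycle (starting with Cycle 2"). Section 10.3 agrees: "The tumor response will be evaluated by CT scans every 2 cycles starting with week 3 of cycle 2". Section 5.4 sets 28-day cycles and adds, in footnote 12, "All study visits allow a +/- 7 day window". That footnote is marked on the Day 1, Day 8/15/22 and Day 15 columns, not on the scan column, although its text covers all visits.
- **Role of the window (10.3).** The section recognises the timing problem: "Six-months since starting treatment are 182 days, may not be on the CT scan date". It says that scans will not be on a strict schedule, and that scans within ±14 days of Day 182 "will be used to determine the 6-month PFS status if there are no other scans available to determine the status". It counts clinical deterioration as progression without a scan.
- **Dating of progression.** The PFS definition in 6.1.7 runs to the time of progression and has no rule for progression between scans. The nearest guidance is indirect. Duration of response (6.1.6) runs "until the first date that recurrent or progressive disease is objectively documented". Footnote 10 of 5.4, for patients who stop treatment for other reasons, has "standard of care scans measured via RECIST until progressive disease, to determine date of disease progression".
- **Supporting analyses (10.3).** PFS at week 24, and a Kaplan-Meier estimate at 6 months.

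**The concern.** The endpoint is a yes/no count at a fixed day, and the planned calendar has no scan near that day. Section 6.1.10 makes the in-window scan the one that decides; Section 10.3 uses it only when nothing else does. A patient without progression at about Day 158 who first shows it at about Day 214 can be scored in three ways:

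1. **By documentation date.** Progression is dated after Day 182, so the patient is a success. The count is then in effect status at about Day 158, plus deaths and clinical progression up to Day 182.
2. **As progression before the landmark, or as unknown.** The patient is a failure. The count is then in effect status at about Day 214.
3. **Strict 6.1.10.** Without an in-window scan the status is unknown, so the patient is a failure even if still progression-free at Day 214.

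The count sets the stage I rule (5 of 11 in cohort A, 7 of 11 in cohort B) and the final rule (14 of 24 and 18 of 24). An unwritten choice between these readings could be made after the data are seen.

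**Working it through.** **Scan days.** Week 3 of cycle c covers Days 28(c−1)+15 to 28(c−1)+21.

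| Cycle | Planned days | With ±7 days |
|---|---|---|
| 2 | 43–49 | 36–56 |
| 4 | 99–105 | 92–112 |
| 6 | 155–161 | 148–168 |
| 8 | 211–217 | 204–224 |

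The window is 182 ± 14 = Days 168–196. No planned day falls in it, and the ±7-day allowance reaches only Day 168. A cumulative delay of 168−161 = 7 to 168−155 = 13 days, depending on the scan day, brings the cycle 6 scan into the window. It stays there up to a delay of 35–41 days.

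**Supporting analyses.** Week 24 is Day 24 × 7 = 168, inside the same Day 161–211 gap. For progression dated at on-schedule scans it therefore draws on the same scans as the Day 182 count. No scan window is given for week 24; with ±14 days (Days 154–182) the cycle 6 scan would count. The Kaplan-Meier estimate has no on-schedule scan in the gap either. Deaths, clinical progression and delayed scans can still separate the two dates.

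**The plan's own figures (10.1, 10.2).** For success probability q, stage I threshold c1 and final threshold c:

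P(promising) = Σ over x = c1 to 11 of Bin(x; 11, q) × P(Bin(13, q) ≥ c − x)

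- A (c1 = 5, c = 14): 0.0514 at q = 0.40 and 0.805 at q = 0.65.
- B (c1 = 7, c = 18): 0.0531 at q = 0.57 and 0.801 at q = 0.80.

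These reproduce the stated 5.1%, 5.3% and 80%.

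**Illustration.** Assume exponential PFS and that the design rates p are true Day 182 rates. Status read at Day d then has rate q = p^(d/182).

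| Status read at | Null rate A / B | Type I error A / B | Power A / B |
|---|---|---|---|
| Day 182 (design) | 0.400 / 0.570 | 5.1% / 5.3% | 80.5% / 80.1% |
| Day 158 (reading 1) | 0.451 / 0.614 | 13.2% / 11.8% | 89.6% / 87.7% |
| Day 214 (reading 2) | 0.340 / 0.516 | 1.2% / 1.6% | 64.7% / 68.0% |

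On reading 1, expected null events between Days 158 and 182 are 24 × (0.4514 − 0.40) = 1.23 patients in A and 24 × (0.6139 − 0.57) = 1.05 in B. With none of them caught, the chance that an ineffective drug passes stage I goes from 47% to 61% (A) and from 45% to 57% (B).

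Reading 3 is not sized. If every patient were on schedule, almost none could count as a success, whatever the drug does.

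**How far reading 1 moves with its assumptions (type I error, A / B).**
- Scan on Day 155: 14.7% / 12.9%. Day 161: 11.8% / 10.7%.
- Weibull PFS, shape 0.7: 10.2% / 9.5%. Shape 1.5: 19.3% / 16.4%.
- A quarter of patients with a Day 182 scan: 10.7% / 9.8%. Half: 8.5% / about 8%. Three quarters: 6.7% / 6.6%. Catching the same shares of the interval events as deaths or clinical progression gives the same figures.
- 5% of otherwise successful patients scored as failures for withdrawal or loss (assumed): 9.0% / 6.9%. At 10%: 5.8% / 3.7%. Power also falls.

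**The case against.** The strongest reply is that the plan saw the problem. Section 10.3 says that Day 182 may not be a scan date, allows other scans to settle status, counts clinical deterioration, and adds a week 24 analysis. Dose delays are allowed and scans are not strictly scheduled, so some patients will have an in-window scan. Counting withdrawals and losses as failures works against inflation. The null and alternative rates come from another trial (10.1) whose scan schedule is not given; if its scans were similarly spaced, the comparison could be fair as it stands.

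Most of this stands as a limit on the size of the effect. It does not remove the defect. Recognising the mismatch does not say how to score the patient caught between the two scans. Sections 6.1.10 and 10.3 still give the window different roles, and week 24 lies in the same gap.

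A reader might infer that the trial's type I error is 13.2% and 11.8%, or at most that. The documents do not support this. Those figures belong to one reading and one model, and the sensitivity results fall on both sides of them. The documentation-date reading is the better supported of the three, but its support is indirect: 6.1.6 concerns duration of response, and footnote 10 concerns patients who stop treatment for reasons other than progression. A reader might also infer that the mismatch always favours a promising result. It does so on reading 1 only; reading 2 lowers both type I error and power.

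**Conclusion.** The point holds and should be fixed. Two things are certain from the text: an on-schedule patient has no planned scan in Days 168–196 (apart from Day 168 at the edge of the visit allowance), and the two sections that define the primary count treat in-window scans differently. Neither gives an explicit rule for progression first seen at about Day 214. It would be too much to say that no rule applies, since the general rules each yield a score; the trouble is that the scores conflict. It would also be too much to say that no patient can have an in-window scan. How many will is unknown.

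The effect on error rates is conditional, in size and in direction. With exponential PFS and design rates that are true Day 182 rates, the choice between readings 1 and 2 moves type I error between 13.2% and 1.2% in cohort A and between 11.8% and 1.6% in cohort B. Power moves between about 90% and 65% in A, and between about 88% and 68% in B. Delays, extra scans, clinically detected events and withdrawals counted as failures reduce the reading 1 figures. Similarly scheduled historical rates could remove the shift.

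**What to change.** Before stage I is read:

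1. **Calendar (5.2.5, 5.4, 10.3).** Time tumour assessments from first dose, regardless of dose delays, so that the third falls within Day 182 ± 14. Re-space the first two, for example about Days 61, 121 and 182 (gaps of 60 and 61 days).
2. **One identical rule in 6.1.10 and 10.3.** Progression or death on or before the landmark scan is a failure. A progression-free landmark scan is a success, as is a progression-free later scan if the landmark scan was missed. Progression first seen on a later scan with no in-window scan is a failure, in line with the plan's handling of unknown status. Add a sensitivity analysis by documentation date.

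On the same model, with third scans spread evenly over Days 168–196, type I error is 5.2% / 5.3% and power 80.5% / 80.2%. If 10% also miss that scan and are next scanned at about Day 242 (assumed), the figures are 4.1% / 4.4% and 78% / 78%. The failure rule should come only with the calendar change: on the current calendar it is reading 2, with power 65% / 68%.

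Cost: a small amendment, with no extra patients and no extra scans by the landmark. The first scan moves from about Day 46 to about Day 61, so the earliest progressions may be seen up to about 15 days later. Scans may need appointments separate from cycle visits.

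If the calendar cannot change, write one documentation-date rule in both sections and report the result as status at the last scan before Day 182.

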6.2 Safety/tolerability

Analyses of safety/ toxicity will be performed for all patients having received at least one dose of study drug. The study will use the CTCAE version 4 for reporting of non-hematologic adverse events (<http://ctep.cancer.gov/reporting/ctc.html>) and modified criteria for hematologic adverse events.

7.1 ADVERSE EVENTS

7.1 Adverse Event Monitoring

Adverse event data collection and reporting, which are required as part of every clinical trial, are done to ensure the safety of Subjects enrolled in the studies as well as those who will enroll in future studies using similar agents. Adverse events are reported in a routine manner at scheduled times during a trial. Additionally, certain adverse events must be reported in an expedited manner to allow for optimal monitoring of patient safety and care.

All patients experiencing an adverse event, regardless of its relationship to study drug, will be monitored until:

- the adverse event resolves or the symptoms or signs that constitute the adverse event return to baseline;
- any abnormal laboratory values have returned to baseline;
- there is a satisfactory explanation other than the study drug for the changes observed; or
- death.

7.2 Definitions

7.2.1 Definition of Adverse Event

An adverse event (AE) is any untoward medical occurrence in a patient receiving study treatment and which does not necessarily have a causal relationship with this treatment. An AE can therefore be any unfavorable and unintended sign (including an abnormal laboratory finding), symptom, or disease temporally associated with the use of an experimental intervention, whether or not related to the intervention.

7.2.2 Severity of Adverse Events

All adverse events will be graded according to the NCI Common Terminology Criteria for Adverse Events (CTCAE) version 4.0. The CTCAE v4 is available at <http://ctep.cancer.gov/reporting/ctc.html>

If no CTCAE grading is available, the severity of an AE is graded as follows:

Mild (grade 1): the event causes discomfort without disruption of normal daily activities.

Moderate (grade 2): the event causes discomfort that affects normal daily activities.

Severe (grade 3): the event makes the patient unable to perform normal daily activities or significantly affects his/her clinical status.

Life-threatening (grade 4): the patient was at risk of death at the time of the event.

Fatal (grade 5): the event caused death.

7.2.3 Serious Adverse Events

A “serious” adverse event is defined in regulatory terminology as any untoward medical occurrence that:

7.3.3.1 Results in death.

If death results from (progression of) the disease, the disease should be reported as event (SAE) itself.

7.3.3.2 Is life-threatening.

(the patient was at risk of death at the time of the event; it does not refer to an event that hypothetically might have caused death if it were more severe).

7.3.3.3 Requires in-patient hospitalization or prolongation of existing hospitalization for ≥ 24 hours.

7.3.3.4 Results in persistent or significant disability or incapacity.

7.3.3.5 Is a congenital anomaly/birth defect

7.3.3.6 Is an important medical event

Any event that does not meet the above criteria, but that in the judgment of the investigator jeopardizes the patient, may be considered for reporting as a serious adverse event. The event may require medical or surgical intervention to prevent one of the outcomes listed in the definition of “Serious Adverse Event”.

For example: allergic bronchospasm requiring intensive treatment in an emergency room or at home; convulsions that may not result in hospitalization; development of drug abuse or drug dependency.

7.3 Steps to Determine If an Adverse Event Requires Expedited Reporting

Step 1: Identify the type of adverse event using the NCI Common Terminology Criteria for Adverse Events (CTCAE v4).

Step 2: Grade the adverse event using the NCI CTCAE v4.

Step 3: Determine whether the adverse event is related to the protocol therapy
Attribution categories are as follows:

- Definite – The AE *is clearly related* to the study treatment.
- Probable – The AE *is likely related* to the study treatment.
- Possible – The AE *may be related* to the study treatment.
- Unlikely—The AE *is unlikely related* to the study treatment.
- Unrelated – The AE *is clearly NOT related* to the study treatment.

Note: This includes all events that occur within 30 days of the last dose of protocol treatment. Any event that occurs more than 30 days after the last dose of treatment and is attributed (possibly, probably, or definitely) to the agent(s) must also be reported accordingly.

Step 4: Determine the prior experience of the adverse event.

Expected events are those that have been previously identified as resulting from administration of the agent. An adverse event is considered unexpected, for expedited reporting purposes only, when either the type of event or the severity of the event is not listed in:

- the drug package insert;
- the current Investigator’s Brochure

7.4 Reporting Requirements for Adverse Events

7.4.1 Expedited Reporting

- The Principal Investigator must be notified within 24 hours of learning of any serious adverse events, regardless of attribution, occurring during the study or within 30 days of the last administration of the study drug.
 - Study Chair/USC PI: [name] ([contact])
 - Multi-site Coord./DSMC Coord.: [name] ([contact])
- SAE occurring after consent but before first dose will not require reporting.
- **The Investigator may report serious adverse drug reactions (SADRs) using either:**

A MedWatch form available at <http://www.fda.gov/medwatch/>

All reports shall be sent electronically to:

Electronic Mailbox: [contact]

[contact]

Address: Global Pharmacovigilance - USA
Mail only: Bayer HealthCare Pharmaceuticals Inc.
[name]
[name]

Address: [name]
FDX or UPS only

Reports for all Bayer products can also be phoned in via our Clinical Communications Dept:

[contact]

The investigator must report to Bayer any pregnancy occurring in a study subject, or in his partner, during the subject's participation in this study. The report should be submitted within the same timelines as an SAE, although a pregnancy per se is not considered an SAE.

For a study subject, the outcome of the pregnancy should be followed up carefully, and any abnormal outcome of the mother or the child should be reported.

For the pregnancy of a study subject's partner, all efforts should be made to obtain similar information on course and outcome, subject to the partner's consent.

Progressive disease

If progressive disease leads to signs and symptoms that meet the criteria for an SAE (i.e., hospitalization, disability, death, or important medical event), the signs and symptoms should be reported as an SAE to Bayer and not the underlying progressive disease.

Death

If any subject dies during the trial or within 30 days of the end-of-treatment visit, the investigator will inform Bayer and record the cause of death in detail (within 24 hours).

All non-USC sites are required to notify the study chair, [name] and the multi-site coordinator of all SAE submissions. Investigators should also report events to their IRB as required.

SAE notification to the FDA:

- USC: study team to work with CISO QA to submit to the FDA using MedWatch 3500A form in accordance within the FDA required timelines

-
- Non-USC site: study team to notify USC PI within 24hrs of site becoming aware of the event by completing a MedWatch 3500A form. USC will review and submit applicable reports to the FDA and notify Bayer of the FDA submission.

The study sponsor, USC, will be responsible for notifying FDA of any unexpected fatal or life-threatening suspected adverse reaction as soon as possible but in no case later than 7 calendar days after the sponsor's initial receipt of the information.

IRB reporting

- The Institutional IRB must be notified of “any unanticipated problems involving risk to subjects or others” in accordance with the Institutional policy. Such policies will be provided to the CISO QA prior to enrolling 1st patient. The following events meet the definition of UPR:
 1. Any serious event (injuries, side effects, deaths or other problems), which in the opinion of the Principal Investigator was unanticipated, involved risk to subjects or others, and was possibly related to the research procedures.
 2. Any serious accidental or unintentional change to the IRB-approved protocol that alters the level of risk.
 3. Any deviation from the protocol taken without prior IRB review to eliminate apparent immediate hazard to a research subject.
 4. Any new information (e.g., publication, safety monitoring report, updated sponsor safety report), interim result or other finding that indicates an unexpected change to the risk/benefit ratio for the research.
 5. Any breach in confidentiality that may involve risk to the subject or others.
 6. Any complaint of a subject that indicates an unanticipated risk or that cannot be resolved by the Principal Investigator.
- The USC NCCC Data and Safety Monitoring Committee (DSMC) must be notified within 24 hours of submission of such reportable event to the IRB. The patient ID and the study number as well as identifier of the SAE report should be submitted to the DSMC Coordinator via email or Fax to the attention of the DSMC Coordinator at [contact].
- The FDA should be notified within 7 business days of any unexpected fatal or life-threatening adverse event with possible relationship to study drug, and 15 business days of any event that is considered: 1) serious, 2) unexpected, and 3) at least possibly related to study participation.

